# 6.3.3 Response Criteria

# 6.3.3.1 Evaluation of Target Lesions

Complete Response (CR): Disappearance of all target lesions. Any pathological lymph nodes (whether target or non-target) must have reduction in short axis to <10 mm.

Partial Response (PR): At least a 30% decrease in the sum of the diameters of target lesions, taking as reference the baseline sum of diameters.

Progressive Disease (PD): At least a 20% increase in the sum of the diameters of target lesions, taking as reference the smallest sum on study (this includes the baseline sum if that is the smallest on study). In addition to the relative increase of 20%, the sum must also demonstrate an absolute increase of at least 5 mm. (Note: the appearance of one or more new lesions is also considered progressions).

Stable Disease (SD): Neither sufficient shrinkage to qualify for PR nor sufficient increase to qualify for PD, taking as reference the smallest sum of diameters while on study.

# 6.3.3.2 Evaluation of Non-Target Lesions

Complete Response (CR): Disappearance of all non-target lesions and normalization of tumor marker level. All lymph nodes must be non-pathological in size (<10 mm short axis).

**Note:** If tumor markers are initially above the upper normal limit, they must normalize for a patient to be considered in complete clinical response.

Non-CR/Non-PD: Persistence of one or more non-target lesion(s) and/or maintenance of tumor marker level above the normal limits.

Progressive Disease (PD): Appearance of one or more new lesions and/or *unequivocal progression* of existing non-target lesions. *Unequivocal progression* should not normally trump target lesion status. It must be representative of overall disease status change, not a single lesion increase.

Although a clear progression of "non-target" lesions only is exceptional, the opinion of the treating physician should prevail in such circumstances, and the progression status should be confirmed at a later time by the review panel (or Principal Investigator).

# 6.3.3.3 Evaluation of Best Overall Response

The best overall response is the best response recorded from the start of the treatment until disease progression/recurrence (taking as reference for progressive disease the smallest measurements recorded since the treatment started). The patient's best response assignment will depend on the achievement of both measurement and confirmation criteria.

Target Lesions	Non-Target Lesions	New Lesions	Overall Response	Best Overall Response when Confirmation is Required*
CR	CR	No	CR	$\geq$ 4 wks. Confirmation**
CR	Non- CR/Non-PD	No	PR	
CR	Not evaluated	No	PR	≥4 wks. Confirmation**
PR	Non- CR/Non- PD/not evaluated	No	PR	
SD	Non- CR/Non- PD/not evaluated	No	SD	Documented at least once $\geq 4$ wks. from baseline**
PD	Any	Yes or No	PD	no mion SD_DD_on CD
Any	PD***	Yes or No	PD	no prior SD, PR or CR

For Patients with Measurable Disease (i.e., Target Disease)

Target Lesion	0	New Lesions	Overall Response	Best Overall Response when Confirmation is Required*	
Any	Any	Yes	PD		
**	Only for non-randomize	ed trials with re	esponse as prima		
	In exceptional circumstances, unequivocal progression in non-target lesions may be accepted as disease progression.				
	objective evidence of	disease progreeffort should	ession at that t	uiring discontinuation of treatment without ime should be reported as " symptomatic iment the objective progression even after	

For Patients with Non-Measurable Disease (i.e., Non-Target Disease)

No	CR
No	Non-CR/non-PD*
No	not evaluated
Yes or No	PD
Yes	PD
	No       No       Yes or No

\* 'Non-CR/non-PD' is preferred over 'stable disease' for non-target disease since SD is increasingly used as an endpoint for assessment of efficacy in some trials so to assign this category when no lesions can be measured is not advised

# 6.3.4 Duration of Response

Duration of overall response: The duration of overall response is measured from the time measurement criteria are met for CR or PR (whichever is first recorded) until the first date that recurrent or progressive disease is objectively documented (taking as reference for progressive disease the smallest measurements recorded since the treatment started).

The duration of overall CR is measured from the time measurement criteria are first met for CR until the first date that progressive disease is objectively documented.

Duration of stable disease: Stable disease is measured from the start of the treatment until the criteria for progression are met, taking as reference the smallest measurements recorded since the treatment started, including the baseline measurements.

# 6.3.5 Progression-Free Survival (PFS)

PFS is defined as the duration of time from start of treatment to time of progression or death, whichever occurs first.

#### 6.4 TOXICITY CRITERIA

The following adverse event management guidelines are intended to ensure the safety of each patient while on the study. The descriptions and grading scales found in the revised NCI Common Terminology Criteria for Adverse Events (CTCAE) version 5 will be utilized for AE reporting. All appropriate treatment areas should have access to a copy of the CTCAE version 5. A copy of the CTCAE version 5 can be downloaded from the CTEP web site: http://ctep.cancer.gov/protocolDevelopment/electronic applications/ctc.htm#ctc

# 7 SAFETY REPORTING REQUIREMENTS/DATA AND SAFETY MONITORING PLAN

# 7.1 **DEFINITIONS**

# 7.1.1 Adverse Event

Any untoward medical occurrence in a human subject, including any abnormal sign (for example, abnormal physical exam or laboratory finding), symptom, or disease, temporally associated with the subject's participation in research, whether or not considered related to the subject's participation in the research.

#### 7.1.2 Suspected adverse reaction

Suspected adverse reaction means any adverse event for which there is a reasonable possibility that the drug caused the adverse event. For the purposes of IND safety reporting, 'reasonable possibility' means there is evidence to suggest a causal relationship between the drug and the adverse event. A suspected adverse reaction implies a lesser degree of certainty about causality than adverse reaction, which means any adverse event caused by a drug.

# 7.1.3 Unexpected adverse reaction

An adverse event or suspected adverse reaction is considered "unexpected" if it is not listed in the investigator brochure or is not listed at the specificity or severity that has been observed; or, if an investigator brochure is not required or available, is not consistent with the risk information described in the general investigational plan or elsewhere in the current application. "Unexpected" also refers to adverse events or suspected adverse reactions that are mentioned in the investigator brochure as occurring with a class of drugs or as anticipated from the pharmacological properties of the drug, but are not specifically mentioned as occurring with the particular drug under investigation.

# 7.1.4 Serious

An Unanticipated Problem or Protocol Deviation is serious if it meets the definition of a Serious Adverse Event or if it compromises the safety, welfare or rights of subjects or others.

# 7.1.5 Serious Adverse Event

An adverse event or suspected adverse reaction is considered serious if in the view of the investigator or the sponsor, it results in any of the following:

- Death,
- A life-threatening adverse drug experience
- Inpatient hospitalization or prolongation of existing hospitalization
- Persistent or significant incapacity or substantial disruption of the ability to conduct normal life functions
- A congenital anomaly/birth defect.
- Important medical events that may not result in death, be life-threatening, or require hospitalization may be considered a serious adverse drug experience when, based upon appropriate medical judgment, they may jeopardize the patient or subject and may require medical or surgical intervention to prevent one of the outcomes listed in this definition.

# 7.1.6 Disability

A substantial disruption of a person's ability to conduct normal life functions.

# 7.1.7 Life-threatening adverse drug reaction

Any adverse event or suspected adverse reaction that places the patient or subject, in the view of the investigator or sponsor, at immediate risk of death from the reaction as it occurred, i.e., it does not include a reaction that had it occurred in a more severe form, might have caused death.

# 7.1.8 **Protocol Deviation (NIH Definition)**

Any change, divergence, or departure from the IRB-approved research protocol.

# 7.1.9 Non-Compliance (NIH Definition)

The failure to comply with applicable NIH Human Research Protections Program (HRPP) policies, IRB requirements, or regulatory requirements for the protection of human research subjects.

# 7.1.10 Unanticipated Problem

Any incident, experience, or outcome that:

- Is unexpected in terms of nature, severity, or frequency in relation to

   (a) the research risks that are described in the IRB-approved research protocol and informed consent document; Investigator's Brochure or other study docu-ments, and
   (b) the characteristics of the subject population being studied; AND
- Is related or possibly related to participation in the research; AND
- Suggests that the research places subjects or others at a *greater risk of harm* (including physical, psychological, economic, or social harm) than was previously known or recognized.
- 7.2 NIH IRB AND CLINICAL DIRECTOR (CD) REPORTING

# 7.2.1 NIH IRB and NCI CD Expedited Reporting of Unanticipated Problems and Deaths

The Protocol PI will report in the NIH Problem Form to the NIH IRB and NCI CD:

• All deaths, except deaths due to progressive disease

*Abbreviated Title: Ad5-based vaccines in mCRPC NCI Version Date:* 09.20.2018

- All Protocol Deviations
- All Unanticipated Problems
- All non-compliance

Reports must be received within 7 days of PI awareness via iRIS.

# 7.2.2 NIH IRB Requirements for PI Reporting at Continuing Review

The protocol PI will report to the NIH IRB:

- 1. A summary of all protocol deviations in a tabular format to include the date the deviation occurred, a brief description of the deviation and any corrective action.
- 2. A summary of any instances of non-compliance
- 3. A tabular summary of the following adverse events:
  - All Grade 2 **unexpected** events that are possibly, probably or definitely related to the research;
  - All Grade 3 and 4 events that are possibly, probably or definitely related to the research;
  - All Grade 5 events regardless of attribution;
  - All Serious Events regardless of attribution.

**NOTE**: Grade 1 events are not required to be reported.

# 7.2.3 NIH IRB Reporting of IND Safety Reports

Only IND Safety Reports that meet the definition of an unanticipated problem will need to be reported to the NIH IRB.

# 7.3 IND SPONSOR REPORTING CRITERIA

During the first 30 days after the subject receives investigational agent, the investigator must **immediately** report to the sponsor, using the mandatory MedWatch form 3500a or equivalent, any serious adverse event, whether or not considered drug related, including those listed in the protocol or investigator brochure and must include an assessment of whether there is a reasonable possibility that the drug caused the event. For serious adverse events that occur more than 30 days after the last administration of investigational agent/intervention, only report those that have an attribution of at least possibly related to the agent/intervention.

Required timing for reporing per the above guideline:

- Deaths (except death due to progressive disease) must be reported via email within 24 hours. A complete report must be submitted within one business day.
- Other serious adverse events as well as deaths due to progressive disease must be reported within one business day

Events will be submitted to the Center for Cancer Research (CCR) at: [contact] and to the CCR PI and study coordinator.

# 7.3.1 Reporting Pregnancy

# 7.3.1.1 Paternal exposure

Male patients should refrain from fathering a child or donating sperm during the study and for one month after the last dose of study vaccines. Pregnancy of the patient's partner is not considered to be an AE. However, the outcome of all pregnancies (spontaneous miscarriage, elective termination, ectopic pregnancy, normal birth, or congenital abnormality) occurring from the date of the first dose until one month after the last dose should, if possible, be followed up and documented.

7.4 SAFETY REPORTING CRITERIA TO THE PHARMACEUTICAL COLLABORATORS

# 7.4.1 Etubics Corporation (ETBX-051, ETBX-061, ETBX-071)

All events listed below must be reported in the defined timelines to [contact].

The CCR Office of Regulatory Affairs will send all reports to the manufacturer as described below.

In the event of any new SAE (of any Grade) occurring during the reporting period (from first dose until decision made to discontinue treatment), the investigator must immediately (i.e., within a maximum 2 business days after becoming aware of the event) inform the Manufacturer (Etubics Corporation) or designee by telephone, by fax, or by email.

When an event (or follow-up information) is reported by telephone, a written report must be sent immediately thereafter by fax or email.

Reporting procedures and timelines are the same for any new information on a previously reported SAE (=follow-up). Any new SAE is reported to:

[name] VP Operations [name] [contact] [contact] (primary number) [contact] Email: [contact]

All Medwatch 3500a forms and written reports should be transmitted, which must be completed by the investigator following specific completion instructions. Relevant pages from the CRF may be provided in parallel (e.g., medical history, concomitant drugs).

In all cases, the information provided in the SAE Report Form must be consistent with the data on the event that is recorded in the corresponding sections of the CRF.

# 7.5 INSTITUTIONAL BIOSAFETY COMMITTEE (IBC) REPORTING CRITERIA

# 7.5.1 Serious Adverse Event Reports to IBC

The Principal Investigator (or delegate) will notify IBC of any unexpected fatal or life-threatening experience associated with the use of ETBX-071, ETBX-061, and ETBX-051vaccines as soon as

possible but in no event later than 7 calendar days of initial receipt of the information. Serious adverse events that are unexpected and associated with the use of the ETBX-071, ETBX-061, and ETBX-051vaccines, but are not fatal or life-threatening, much be reported to the NIH IBC as soon as possible, but not later than 15 calendar days after the investigator's initial receipt of the information. Adverse events may be reported by using the FDA Form 3500a.

# 7.5.2 Annual Reports to IBC

Within 60 days after the one-year anniversary of the date on which the IBC approved the initial protocol, and after each subsequent anniversary until the trial is completed, the Principal Investigator (or delegate) shall submit the information described below. Alternatively, IRB continuing review report can be sent to the IBC in lieu of a separate report. Please include the IBC protocol number on the report.

# 7.5.2.1 Clinical Trial Information

A brief summary of the status of the trial in progress or completed during the previous year. The summary is required to include the following information:

- the title and purpose of the trial
- clinical site
- the Principal Investigator
- clinical protocol identifiers;
- participant population (such as disease indication and general age group, e.g., adult or pediatric);
- the total number of participants planned for inclusion in the trial; the number entered into the trial to date whose participation in the trial was completed; and the number who dropped out of the trial with a brief description of the reasons
- the status of the trial, e.g., open to accrual of subjects, closed but data collection ongoing, or fully completed,
- if the trial has been completed, a brief description of any study results.

7.5.2.2 Progress Report and Data Analysis

Information obtained during the previous year's clinical and non-clinical investigations, including:

- a narrative or tabular summary showing the most frequent and most serious adverse experiences by body system
- a summary of all serious adverse events submitted during the past year
- a summary of serious adverse events that were expected or considered to have causes not associated with the use of the gene transfer product such as disease progression or concurrent medications
- if any deaths have occurred, the number of participants who died during participation in the investigation and causes of death
- a brief description of any information obtained that is pertinent to an understanding of the gene transfer product's actions, including, for example, information about dose-response, information from controlled trials, and information about bioavailability.

# 7.6 DATA AND SAFETY MONITORING PLAN

# 7.6.1 Principal Investigator/Research Team

The clinical research team will meet on a regular basis when patients are being actively treated on the trial to discuss each patient, enrollment and data management issues. Decisions about dose level enrollment and dose de-escalation will be made based on the toxicity data from prior patients.

All data will be collected in a timely manner and reviewed by the principal investigator. Adverse events will be reported as required above. Any safety concerns, new information that might affect either the ethical and or scientific conduct of the trial, or protocol deviations will be immediately reported to the IRB using iRIS.

The principal investigator will review adverse event and response data on each patient to ensure safety and data accuracy. The principal investigator will personally conduct or supervise the investigation and provide appropriate delegation of responsibilities to other members of the research staff.

# 7.6.2 Sponsor Monitoring Plan

As a sponsor for clinical trials, FDA regulations require the CCR to maintain a monitoring program. The CCR's program allows for confirmation of: study data, specifically data that could affect the interpretation of primary study endpoints; adherence to the protocol, regulations, and SOPs; and human subjects protection. This is done through independent verification of study data with source documentation focusing on:

- Informed consent process
- Eligibility confirmation
- Drug administration and accountability
- Adverse events monitoring
- Response assessment.

The monitoring program also extends to multi-site research when the CCR is the coordinating center.

This trial will be monitored by personnel employed by an CCR contractor. Monitors are qualified by training and experience to monitor the progress of clinical trials. Personnel monitoring this study will not be affiliated in any way with the trial conduct.

# 7.6.3 Safety Monitoring Committee (SMC)

This protocol will require oversight from the Safety Monitoring Committee (SMC). Initial review will occur as soon as possible after the annual NIH IRB continuing review date. Subsequently, each protocol will be reviewed as close to annually as the quarterly meeting schedule permits or more frequently as may be required by the SMC. For initial and subsequent reviews, protocols will not be reviewed if there is no accrual within the review period. Written outcome letters will be generated in response to the monitoring activities and submitted to the Principal investigator and Clinical Director or Deputy Clinical Director, CCR, NCI.

# 8 STATISTICAL CONSIDERATIONS

#### 8.1 STATISTICAL HYPOTHESES

#### 8.1.1 Primary Endpoints

- Safety and tolerability of the recommended phase 2 dose of PSA/MUC1/Brachyury vaccine as determined by the fraction of patients who experience a DLT.
- Dose-limiting toxicities (DLTs) and maximum tolerated dose (MTD)
- Treatment-emergent adverse event (AEs) and serious adverse events (SAEs).
- Clinically significant changes in safety laboratory tests, physical examinations, electrocardiograms (ECGs), and vital signs.

# 8.1.2 Secondary Efficacy Endpoints

Preliminary assessments of:

- objective response rate (ORR) percentage of subjects who experience partial or complete response at any time point during treatment period
- disease control rate (DCR) –percentage of subjects who experience partial response, complete response or stable disease lasting for at least 6 months
- duration of response the time from when measurement criteria for PR or CR are met until disease recurrence or progression per dose cohort and overall
- progression-free survival (PFS) the time from the date of first treatment to the date of disease progression or death (any cause) whichever occurs first per dose cohort
- overall survival (OS) the time from the date of first treatment to the date of death (any cause) per dose cohort and overall
- PSA doubling time (PSADT) week 14 and at the end of study treatment in subjects with advanced cancer treated with the ETBX-071, ETBX-061, and ETBX-051 vaccines

effect size of 1.5 (1.5 SDs of the measure of interest, assumed to be approximately the same in responders and non-responders), when there are 3 responders and 9 non-responders (total of 12 evaluable patients). With 4 responders and 8 non-responders, the same comparison would have 85% power. In practice, an exact Wilcoxon rank sum test will be used instead of a two-group t-test.

To accrue a total of 18 evaluable patients, it is expected that up to 2 years may be required. Since up to three dose levels may be explored, in addition to the 12 evaluable patients at the MTD, the accrual ceiling will be set at 30 patients.

#### 8.3 POPULATIONS FOR ANALYSIS

# 8.3.1 Definitions

Evaluable for toxicity: All patients will be evaluable for toxicity from the time of their first treatment with ETBX vaccines.

Evaluable for DLT: The first 6 - 18 subjects enrolled will be evaluable for DLT from the time of their first treatment with ETBX-vaccines until 28 days have passed. Subjects who do not complete the DLT observation period for reasons other than a DLT will be replaced.

Evaluable for objective response: Only those patients who have measurable disease present at baseline, have received at least one dose of therapy, and have had their disease re-evaluated will be considered evaluable for response. These patients will have their response classified according to the definitions stated below.

Evaluable Non-Target Disease Response: Patients who have lesions present at baseline that are evaluable but do not meet the definitions of measurable disease, have received at least one dose of therapy, and have had their disease re-evaluated will be considered evaluable for non-target disease. The response assessment is based on the presence, absence, or unequivocal progression of the lesions.

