## 1.2.6.1 Clinical Safety

[figure not shown]
Etubics Corporation has performed a Phase I/II clinical trial (IND#14325) with an Ad5 [E1-, E2b-]-based vector containing a modified carcinoembryonic antigen (Ad5 [E1-, E2b-]-CEA(6D)) for the immunotherapy of CEA expressing cancer. (2, 3) The Phase I/II study consisted of a doseescalation study of four dosage levels (1x10^9, 1x10^10, 1x10^11, 5x10^11 VP/dose) of ETBX-011 (Phase I component), and the maximally tolerated dose of ETBX-011 (Phase II and  $5 \times 10^{11}$ VP/dose components). Ad5 [E1-, E2b-]-CEA(6D) was administered by SC injection every 3 weeks. Thirty-two patients with metastatic colorectal cancer (mCRC), median age 57.5 (range 38-77) who had failed a median of three prior chemotherapeutic regimens (range 2-5), had a Karnofsky performance status of 90 (range 70-100), and had three sites of metastatic disease (range 1–4), were enrolled. The majority of patients were able to receive all three immunizations. Four patients who stopped immunizations early did so due to significant disease progression. A total of 94 immunization treatments was administered to all patients. There was no dose-limiting toxicity and no serious adverse effects (SAE) that resulted in treatment discontinuation at any vaccine dose level. The most common toxicity was a self-limited, injection site reaction. Other reactions occurred with less than a 10% incidence of all adverse effects (AE) reported and included fever, flu-like symptoms, anorexia, chills, nausea, and headache. These symptoms were also selflimiting and did not require intervention other than symptomatic measures such as acetaminophen.(2, 3)

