# 3.4 STUDY CALENDAR

Assessment	Screening 	Treatment (Every 3-W	Treatment (Every 3-Week Dosing)	g)	Bi-monthly Boosters (every 8 weeks – only expansion cohort) p	End of Treatment (within 90 days after the last vaccine) k	Post Study Therapy Follow Up
Study Week	Day -28 to -1	Baseline/ Wk-0	Wk-3	Wk-6	Week 14, 22, 30, 38, 46, 54		
Clinic Visit	X	Х	X	Х	X	X	
Informed Consent 	Х						
Inclusion/Exclusion	Х						
Demographics	Х						
Physical Examination, Height a , Weight, ECOG	Х	$X^{ ho}$	X	Х	Х	Х	
Medical History c	Х	Х					
Concomitant Medications	Х	Х	Х	Х	Х	Х	
Vital Signs d	Х	Х	Х	Х	Х	Х	
12-Lead ECG	Х				Х	X	
Confirm Contraceptive Measures c	Х						
Study Drug Injection/ Injection Site Reaction Monitoring f		Х	X	Х	Х		

41

tle: Ad5-based vaccines in mCRPC	:: 09.20.2018
Abbreviated Title:	NCI Version Date: 6

Assessment	Screening 	Treatment (Every 3-W	Treatment (Every 3-Week Dosing)	g)	Bi-monthly Boosters (every 8 weeks – only expansion cohort) p	End of Treatment (within 90 days after the last vaccine) k	Post Study Therapy Follow Up
Study Week	Day -28 to -1	Baseline/ Wk-0	Wk-3	Wk-6	Week 14, 22, 30, 38, 46, 54		
Dispensation of Subject Diary Card g		X					
Review of Subject Diary Card g			Х				
Tumor Imaging/CT scan and bone scan h	Х				Х		
Urinalysis	$X^{l}$					Х	
Chemistry Panel m	$\mathbf{X}^{\mathrm{l}}$	$\mathbf{X}^{\mathrm{b}}$	Х	Х	Х	X	
CBC, Differential, Platelets	X 	$X^{ ho}$	Х	Х	Х	Х	
Serum PSA and testosterone level	X	Х	X	X	Х	Х	
PT/INR, PTTT	$X^{l}$					Х	
Serum Virology (HIV, HBV, HCV) i	Х						
Adverse Events		Х	Х	Х	Х	Х	
Exploratory Immune Analysis		Х		X	X (only week 14 and 30)	Х	
Telephone Follow Up j							X

itle: Ad5-based vaccines in mCRPC	· 09.20.2018
Title:	Date:
Abbreviated	NCI Version

Assessment	Screening 	Treatment (Every 3-W	Freatment (Every 3-Week Dosing)	d (S	Bi-monthly Boosters (every 8 weeks – only expansion cohort) p	End of Treatment (within 90 days after the last vaccine) k	End of Treatment Post Study (within 90 Therapy Follow days after the Up last vaccine) k
Study Week	Day -28 to -1	Baseline/ Wk-0	Wk-3	Wk-6	Week 14, 22, 30, 38, 46, 54		
Confirmation of diagnosis (path report) n	Х						

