# **3.5.1** Criteria for removal from protocol therapy

- Completion of protocol therapy.
- Clinical or radiographic progression of disease (not including PSA progression). Patients with serological progression alone will remain on treatment at the discretion of the PI.
- Unacceptable Toxicity as listed in section **3.3.1**
- Any serious adverse event that is unexpected relative to the known safety profile of the investigational agents in the opinion of the investigator
- Participant requests to be withdrawn from active therapy
- Investigator discretion

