# 6.3 RESPONSE CRITERIA

For the purposes of this study, patients should be re-evaluated for response at week 14 and every 8 weeks thereafter and at the of study treatment. In addition to a baseline CT and bone scan, confirmatory scans should also be obtained up to 6 (not less than 4) weeks following initial documentation of objective response.

Response and progression will be evaluated in this study using the new international criteria proposed by the revised Response Evaluation Criteria in Solid Tumors (RECIST) guideline (version 1.1; Eisenhauer 2009). Changes in the largest diameter (unidimensional measurement) of the tumor lesions and the shortest diameter in the case of malignant lymph nodes are used in the RECIST criteria.

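### Dosed subjects with measurable disease who are never re-evaluated fall outside the response-evaluable set, so the objective response rate, if computed on that set, can be biased only upward (minor)

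*Combined protocol and SAP*

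**What the plan says.** Section 8.3.1 (Evaluable for objective response) sets three conditions. It begins "Only those patients who have measurable disease present at baseline" and continues with those who "have received at least one dose of therapy, and have had their disease re-evaluated will be considered evaluable for response". Only these patients have a response classified.

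Section 8.1.2 defines ORR as the "percentage of subjects who experience partial or complete response at any time point during treatment period". Section 8.4.3 plans the percentage with confirmed complete or partial response, by dose cohort and overall, with a 95% confidence interval, and treats disease control in a similar manner. Neither section names a denominator or says how a subject without a post-baseline assessment is counted.

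On timing, section 6.3 says that "patients should be re-evaluated for response at week 14 and every 8 weeks thereafter and at the of study treatment"; a word is missing, presumably *end*. In the section 3.4 calendar, the row "Tumor Imaging/CT scan and bone scan" is marked at screening and in the booster column (weeks 14 to 54) and not under End of Treatment. Footnote h to that row refers back to section 6.3 for how imaging is done.

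Section 3.5.1 lists among the reasons for stopping therapy "Clinical or radiographic progression of disease (not including PSA progression".

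**The concern.** Measurable disease and receipt of a dose are settled by the first treatment. Re-evaluation is not: it depends on the subject surviving, being well enough and staying on study until a scan is done. A subject who misses it for one of those reasons has no documented response, yet 8.3.1 takes him out of the denominator when he could be counted as a non-responder. The exclusion never removes a documented responder, so it works in one direction.

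At stake is the reading of the ORR and its interval, and of the disease control rate if it is computed on the same set. Sections 1.2.1 and 1.2.11 foresee later combination trials, for which these rates may serve as background.

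**Working it through.** **Who is lost.** Reading sections 3.5.1, 6.3, 6.3.3.3 and 8.3.1 together, a dosed subject with measurable disease who stops before week 14 falls into one of two groups:

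- Scanned at or after stopping, as 6.3 asks at the end of treatment and as the note on symptomatic deterioration in 6.3.3.3 encourages. He has been re-evaluated, stays in the set, and counts as a non-responder if he has progressed.
- Never re-evaluated (death, too ill, withdrawal). He is outside the set, and no section counts him as a non-responder.

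Only the second group matters. Call its size *k*.

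**The plan's own figures.** No ORR precision or sample size is stated. The only figures built on a responder count are in section 8.2, which supposes a 25–30% response among 12 evaluable patients: 0.25 × 12 = 3.0 and 0.30 × 12 = 3.6, given as 3–4 responders. The accompanying power uses a two-group t-test, effect size 1.5, one-sided 0.10, df = 10 and noncentrality 1.5 × √(n₁n₂/(n₁+n₂)):

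- 3 v 9: noncentrality 1.5 × √(27/12) = 2.25; power 80.9% (stated 80%).
- 4 v 8: noncentrality 1.5 × √(32/12) = 2.45; power 85.6% (stated 85%).

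Both reproduce. They are used here only as the source of 3 responders in 12.

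**Effect on ORR.** Inputs: N = 12 dosed subjects with measurable disease and x = 3 responders (the section 8.2 supposition); k = 1 to 3 (assumed, as the documents give no value); exact Clopper–Pearson 95% intervals (assumed, as section 8.4.3 names no method).

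Rate in all dosed = x/N. Rate in re-evaluated = x/(N − k). Ratio of the two = N/(N − k).

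| k | Rate | 95% CI | Ratio |
|---|---|---|---|
| 0 | 3/12 = 25.0% | 5.5–57.2% | 1.00 |
| 1 | 3/11 = 27.3% | 6.0–61.0% | 1.09 |
| 2 | 3/10 = 30.0% | 6.7–65.2% | 1.20 |
| 3 | 3/9 = 33.3% | 7.5–70.1% | 1.33 |

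**No responders.** The estimate is 0% on either denominator, but the exact upper limit, 1 − 0.025^(1/n), still moves: 26.5% for 0/12 and 30.8% for 0/10.

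**Smaller N.** Bone-only disease is eligible (2.1.1.12) but non-measurable (6.3.1), so fewer than 12 expansion subjects may have measurable disease. The ratio N/(N − k) is larger for smaller N at the same k.

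**The case against.** The strongest reply is that the plan already keeps most early failures. Section 6.3 calls for re-evaluation when treatment ends. The absence of a mark under End of Treatment in the calendar does not cancel this, because footnote h defers to section 6.3. Section 6.3.3.3 asks for effort to document progression even after treatment has stopped. This stands: a reader might infer that everyone who fails before week 14 disappears from the denominator, and the text does not support that.

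A reader might also import a loss rate from the earlier vaccine trial. Section 1.2.6.1 reports that "Four patients who stopped immunizations early did so due to significant disease progression", which is 4/32 = 12.5%, and section 11.1.2 implies that 6/34 = 17.6% did not receive all three doses. These figures count subjects who stopped dosing, not subjects who were never rescanned, and not all six are attributed to progression. The trial was the manufacturer's, in heavily pretreated colorectal cancer. It supplies no value for *k* here.

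Nor do the documents show that the rule strips early failures from the responder v non-responder comparison in section 8.4.9. That section names the 12 expansion patients, not the 8.3.1 set, and separately requires three injections for immune-response evaluability.

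On importance, ORR is a preliminary secondary assessment described as exploratory. The de-escalation rule, the halting guidelines and the 9-of-18 immune-response criterion do not use it, and deaths still count as events in PFS and OS. All of this stands and limits the severity. It does not answer the narrow gap: a dosed subject who is never re-evaluated has no place in the response analysis.

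**Conclusion.** The concern holds in a limited form and is minor. Section 8.3.1 is the only population the plan defines for objective response, so reading it as the ORR denominator is natural, but sections 8.1.2 and 8.4.3 do not say so. On that reading, and compared with the rate in all dosed subjects with measurable disease, excluding the never re-evaluated can only raise the ORR.

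The size rests on an unstated *k*. At 3 responders in 12, each lost subject adds about 2 to 3 percentage points over k = 1 to 3. The shift is small beside an interval running from 5.5% to 57.2%, and the point estimate does not move at all if nobody responds. It is worth correcting because the direction is known in advance and the correction is simple.

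**What to change.** 1. In 8.3.1 and 8.4.3, state that the ORR denominator is all subjects with measurable disease at baseline who received at least one dose, and that those with no post-baseline disease assessment count as non-responders. Refer to this population in 8.1.2.
2. Use the same denominator for the disease control rate, with unassessed subjects counted as not having disease control.
3. Report the rates in re-evaluated subjects as secondary figures, and give the number never re-evaluated with reasons.
4. Reconcile the end-of-treatment re-evaluation in section 6.3 with the imaging row of the section 3.4 calendar. The only post-baseline imaging mark in that row sits in a column headed as applying to the expansion cohort, whereas section 6.3 speaks of patients generally.

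The cost is a few sentences. The denominator change needs no new data. The reported rates may be a few points lower.
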